Unique Protocol ID: 174052

Brief Title: National Institute for Health Research (NIHR) Health Informatics Collaborative Troponin Study (NHIC-Troponin)

Official Title: National Institute for Health Research (NIHR) Health Informatics Collaborative Cardiovascular Project

DATA ACQUISITION AND ANALYSIS PLAN

Author: [name]

Approvers: [name] / [name]

Date: 07/03/2017

Updated: 04/07/2024

Introduction

This document outlines the specifications and procedures for the NIHR Health Informatics Collaborative (NIHR HIC) Cardiovascular research database and defines the processes for the collection of the NIHR HIC Cardiovascular research data and onward sharing with researchers. The central research database is held within Imperial College Healthcare NHS Trust (ICHNT).

Data are collected locally at the following trusts data for all patients receiving a troponin test and submitted pseudonymously to ICHNT:

- Imperial College Healthcare NHS Trust
- University College London Hospitals NHS Foundation Trust
- Oxford University Hospitals NHS Foundation Trust
- Kings College Hospital NHS Foundation Trust
- Guys and St Thomas' Hospital NHS Foundation Trust

This document covers the processes for local collection of data at all sites. The main database and systems are hosted at ICHNT as the lead organisation for the Cardiovascular Theme.

NIHR HIC Cardiovascular Database Definitions

Local data store

Each trust will have a local store of NIHR HIC Cardiovascular data; this collects their information in an identifiable form from clinical systems, the data will then be de-identified within the local NHS Trust. These de-identified data will be passed to the central research database.

Research database

The research database will contain only de-identified information. This database combines the data from each site (including ICHNT) and will be used for the TROP-RISK study.

Procedures for local data collection into local stores

Data will be collected automatically from primary clinical systems within each Trust. NHS staff will enter data into clinical systems during routine clinical care of patients, or data will be generated as a result of clinical tests. Data in the primary clinical systems will be processed in accordance with each Trusts clinical guidelines and subject to local quality and governance procedures. Data will be extracted automatically and validated processes for data extraction, transformation and loading (ETL) have been designed to import the data into the local secure data stores.

Access to Local data stores

Access to identified data will be limited to those justified and approved by the local information governance teams and will always be NHS staff in accordance with the duty of confidentiality required by law. Anonymisation procedures will be automated after implementation.

Local data stores will be the only areas that hold any patient identifiers. De-identification is completed at this stage prior to passing data into any research databases and datasets.

De-identification

The data will be pseudonymised locally within each Trust; anonymisation processes will be automated and set up by NHS staff in accordance with:

- advice from local information governance procedures
- the HIC Standard Operating Procedure (SOP) for data sharing and anonymisation
- the Clinical data transfer policy

The data items summarised in Table 1 will be anonymised. Anonymisation will be approved locally by information governance teams before data are sent externally to ICHNT. De-identified data are then shared in accordance with the overarching data sharing agreement.

Each site will hold two versions of the database, one identifiable and one with de-identified, pseudonymised data. The de-identified version is for use in research and shared with the central research database at ICHNT. The identifiable database is held so that if necessary patients can be re-identified if it is of importance to re-contact the patient via their care team (please refer to 're-contacting patients' section).

NHS numbers and hospital numbers are pseudonymised using locally approved procedures. Names are removed from the dataset and date of birth is transformed to year of birth. Date of death is shared, however is converted in to relevant survival rates on provision of data to researchers. Researchers will never see the full date of

death or be able to calculate it from other information (all dates are provided as delta for first troponin). The provision of date of death has been agreed by each of the information governance offices at each of the sites in the following de-identification and anonymisation protocol for the TROP-RISK STUDY:

- The exact date of death is required to evaluate mortality after diagnosis.
- Patients presenting with acute coronary syndromes have a high frequency of cardiac events and a high short-term mortality rate. An accurate measure of death is therefore required to fully evaluate this.
- To redact the date of death to year only would misrepresent the survival of these patients, particularly for those who survive for less than one year. The clinical leads at our BRCs have underlined the importance of having the date in full for the TROP-RISK study.

Demographic	Anonymisation
Local Identifier	Provided if NHS number is missing
NHS Number	Use local pseudonymisation algorithm (key to be retained at source) Rename field to subject ID
Family Name	To be removed – LOCAL use
Given Name	To be removed – LOCAL use
Date of Birth	YYYY
Date of Death	DD-MM-YYYY

Table 1. Anonymisation of data elements

Data validity and quality

Prior to pseudonymisation within the clinical systems, NHS number, Date of Birth and patient names will be automatically checked to remove duplication of patients. Samples of data will be clinically validated by members of the clinical team to ensure that the transformation process is correct and data are attributed to the correct patients prior to pseudonymisation. After clinical validation is complete, the data will be transformed to a standardised XML format and validated (Figure 1).

[figure not shown]

Figure 1. Data import and validation process.

Data sharing between Trusts

Data are shared in accordance with the SOP for data sharing, as outlined in Section 1.3.2. Data are encrypted in transit via sFTP on the N3 network (Figure 1). The sFTP is set up and hosted by ICHNT.

Procedures for secure research database

Data validity and quality

ICHNT validate the data to ensure that the structure, data items, units and data types are in accordance with the standardised data model. Data will be rejected if validation fails. On rejection, the files will be archived and the data manager will contact the data provider to review the submission and resend once corrected. Once imported into the secure research database, data are subject to clinical validation by Cardiovascular clinical experts; these validations will be completed by the clinical researchers using de-identified data. Data will be reviewed for data completeness, spread and actual data point values. If data appears invalid it will be rejected.

Data quality reports will be generated and provided to the research team and local data provider after each submission. These will be reviewed after each submission to ensure all areas are populated.

Research Database software

The database is built using Microsoft SQL server 2014, Microsoft's principle database management system software. The installation of the software was carried out by certified technical consultants and tested by the trust ICT team and data warehouse team in accordance with Trust ICT procedures and policies.

Database management

The database is fully backed up on a daily basis. The back-ups are standardised for all Trust databases within the Trust data warehouse. Backups can be restored at any

point by warehouse staff. Data are secondary copies from clinical systems; at any point the participating Trusts can re-extract the data from primary sources. Each site will submit data on a quarterly basis to the database. Data integrity checks will be completed to ensure correct structure is maintained and duplicates are not present.

Once entered on the system, data will not be changed. All access will be 'read only' except via exception, approved by the research Informatics Programme Manager and Clinical Leads group.

The database will be managed by the data manager ([name]) and developer ([name]). Database changes are controlled by the research informatics Programme manager ([name]), and are sanctioned by the NIHR HIC Cardiovascular scientific steering committee (Chaired by [name]). All staff are substantive NHS employees at ICHNT.

Data extracts taken for research will be stored within the data warehouse and retained for the period specified in the data request. All information pertinent to the request will be retained and tracked by the data manager.

Data access for research

TROP-RISK STUDY dataset

All analyses for the TROP-RISK STRUDY will be completed on fully de-identified data. This includes further de-identification to remove dates.

A designated clinical researcher ([name]) will freeze a copy of the database on 1st April 2017, so a static dataset can be used for analysis. This will be retained separately from the live database to allow reproducible analyses.

The study dataset will comprise all patients who had a troponin measured at each of the five academic centres between 2010 (2008 for University College Hospital) and 2017.

Dates will be converted to delta dates, with date zero being the date of the first troponin test. All further dates are provided as number of days from date zero. Age will be provided in years, at the time of the first troponin test.

Date of death will be converted to the number of days since date zero. All patients will be retrospectively followed up, using routinely collected data on the NHS Spine Application, Summary Care Record, until death or censoring on 1st April 2017.

Data elements

The database model will include 156 data points, grouped into demographics, emergency department attendance and inpatient episodes, biochemistry, diagnosis, angiography, revascularization, echocardiography and mortality. Diagnostic data will be based on International Statistical Classification of Diseases and Related Health Problems (ICD) discharge codes.

Outcomes

Primary outcome

The primary outcome will be all-cause mortality. The nature if the data sources means that this is the outcome that will be available and it will be available with high fidelity.

Secondary outcomes

The secondary outcomes will be:

- Acute coronary syndrome (ACS) diagnosis (unstable angina, non-ST segment elevation myocardial infarction (NSTEMI), ST-segment elevation myocardial infarction (STEMI))
- Non-ACS diagnosis
- Angiography
- Revascularisation (coronary artery bypass grafting CABG), percutaneous coronary intervention (PCI))

Statistical Methods

Baseline data

Baseline and demographic characteristics will be summarised by standard descriptive summaries:

- means (standard deviation) for continuous variables which are normally distributed
- median (interquartile range) for continuous variables which are not normally distributed
- number (percentage) for categorical variables

Age distribution

The age distribution of patients who have a troponin measured will be compared with that of the general population using the World Health Organisation (WHO) population estimates for the UK.

Troponin data

Assay performance

Each Trust measures either troponin I or T using either contemporary or high-sensitivity assays. These tests yield results in different measurable ranges with unique cut-off points for the 99th percentile of the upper limit of normal (ULN). A summary table of the performance of each assay will be assembled.

Handling of troponin data

The study dataset will comprise all patients who have had a troponin measured at each of the five academic centres between 2010 (2008 for University College Hospital) and 1st April 2017.

In clinical practice, troponin levels are frequently dichotomised into “positive” (meaning above ULN) or “negative”. Troponin levels may have a progressive relationship with prognosis, too, but the shape of this relationship is not known across the full spectrum of values and making the assumption of a linear relationship of mortality with troponin (or log troponin) may not be secure.

For these reasons, we will treat the data in two ways.

1. We will dichotomise the peak troponin level as being either positive or negative based on the ULN for each troponin assay. This makes no assumption of the shape of the relationship.
2. To standardise the many troponin assays, we will scale the results using the ratio of the observed troponin value divided by the ULN for that particular troponin assay. For example, a patient with a troponin value of 96 using an assay which has an ULN of 40 would have a scaled result of $96/40 = 2.4 \text{ xULN}$.

In some hospitals and some assays, troponin values above a certain level are systematically reported as “more than X”. According to what the hospitals have reported so far, the threshold at which the system gives results like this is in all cases very high. In no case does this truncation of results occur below 10,000 xULN. We therefore plan to set the uppermost band to be “>10,000 x ULN”. This ensures that the unavailability of an explicit value does not affect the troponin band into which any result is allocated.

Similarly, no hospital has reported truncating lower values of troponin at a threshold that is higher than $\frac{1}{2} \text{ xULN}$. Therefore, we plan for the lowermost band to be “< $\frac{1}{2} \text{ xULN}$ ”.

Troponin has a marked positive skew. Therefore, we plan for the bands to be spaced not arithmetically but exponentially, with narrow spacing nearer low values, where there is a higher frequency density of troponin values.

Adopting this approach for analysis has the following advantages:

1. It allows the shape of the relationship to be explored without making assumptions about the shape in advance.
2. It allows values documented in the hospital databases as “less than X” or “more than X” to be used correctly in the analysis rather than omitted or have imputed values.
3. The resulting display of the mortality relationship should be easily interpreted and applied by clinicians.

All analyses on troponin will be performed using the peak troponin level. For patients who have a single troponin measurement, the peak troponin will be based on this measurement. In the remainder of the patients who have more than one

troponin test in the same hospital episode, the peak troponin value will be defined as the highest of all measurements.

Relationship between troponin positivity, age and mortality

To assess the association of dichotomous troponin level (above ULN or not) with all-cause mortality, Cox proportional hazards regression modelling will be used. Hazard ratios will be determined for the following age groups: 18-29, 30-39, 40-49, 50-59, 60-69, 70-79, 80-89 and 90+ years. We will also stratify the hazard ratios for troponin positive versus negative groups across these age groups by troponin assay (contemporary versus high-sensitivity troponin assay).

The Kaplan-Meier method will be used to calculate and display cumulative mortality, with positive and negative troponin bands compared using the log-rank statistic.

Relationship between troponin level and mortality

The main analysis of the association of progressively higher troponins with all-cause mortality will be performed without making assumptions about the shape of the relationship, i.e. with Cox proportional hazards regression modelling.

The Kaplan-Meier method will be used to calculate and display cumulative mortality, with troponin bands compared using the log-rank statistic. The results will be stratified according to ACS diagnosis and revascularisation status.

ACS diagnosis

The ICD-10 codes in Table 2 will be used to indicate an ACS diagnosis.

ICD-10 Code	Category
I20.0	Unstable angina
I21.0	Acute transmural myocardial infarction of anterior wall
I21.1	Acute transmural myocardial infarction of inferior wall
I21.2	Acute transmural myocardial infarction of other sites
I21.3	Acute transmural myocardial infarction of unspecified site
I21.4	Acute subendocardial myocardial infarction
I21.9	Acute myocardial infarction, unspecified
I22.0	Subsequent myocardial infarction of anterior wall
I22.1	Subsequent myocardial infarction of inferior wall
I22.8	Subsequent myocardial infarction of other sites
I22.9	Subsequent myocardial infarction of unspecified site
I24.8	Other forms of acute ischaemic heart disease
I24.9	Acute ischaemic heart disease, unspecified

Table 2. ICD-10 codes used to indicate an ACS diagnosis

Revascularisation status

Acute revascularisation will be defined as having PCI or CABG in the time window between 48 hours before and 3 months after the first troponin measurement. This will account for patients who had revascularisation, in particular PCI, as an

emergency prior to their first troponin blood test and to capture revascularisation, in particular CABG, performed as an outpatient following their index admission.

Statistical package

Statistical analyses will be performed using SPSS software version 24 (SPSS Inc., Chicago, Illinois, United States) and the results verified by replicate analysis using R 3.3.2 statistical package (the R Core Team, Vienna, Austria).

Statistical significance

All hypothesis tests will be 2-tailed. A p-value of <0.05 will be considered statistically significant. No correction will be implemented for multiple testing.

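### Can a patient tested at two Trusts enter the pooled Cox analysis as two subjects, and must the plan change because of it?

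*Combined protocol and SAP*

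**What the plan says.** The Research database section says of the central store: "This database combines the data from each site (including ICHNT) and will be used for the TROP-RISK study". Identifiers do not reach it. Under Access to Local data stores: "Local data stores will be the only areas that hold any patient identifiers".

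The De-identification section says: "NHS numbers and hospital numbers are pseudonymised using locally approved procedures". Table 1 adds: "Use local pseudonymisation algorithm (key to be retained at source". The result is renamed as the subject ID. A local identifier is "Provided if NHS number is missing". The same section places all of this under shared governance texts, among them "the HIC Standard Operating Procedure (SOP) for data sharing and anonymisation", which are not part of the documents.

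Duplicates are mentioned twice. Under the first Data validity and quality heading, before pseudonymisation and inside the clinical systems, "NHS number, Date of Birth and patient names will be automatically checked to remove duplication of patients". Under Database management, integrity checks on the central database are also meant to exclude duplicates, but no matching field is named.

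Follow-up runs from the first troponin test (TROP-RISK STUDY dataset section). All-cause mortality is analysed by Cox regression, with Kaplan-Meier curves and the log-rank test (Statistical Methods). No clustering or robust variance is mentioned.

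**The concern.** Put together, these sections leave a visible hole. If each Trust uses its own algorithm and key, one NHS number yields different subject IDs at different Trusts. A check for duplicate IDs would then pass both rows. The check on names and NHS number comes earlier and, as written, works within a Trust. After de-identification, names are gone and date of birth is cut to the year, so little is left to match on.

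A person seen at two of the five Trusts would then contribute two rows. Each would have its own date zero and peak troponin, possibly from different assays, and both would carry the same death. Three things would be at stake:

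- **Precision.** The model counts the rows as independent, so standard errors are too small.
- **Weighting.** People who attend several Trusts count more than once.
- **Stratification.** A PCI or CABG at the other Trust could be missed in the window from 48 hours before to 3 months after the first test. This matters mainly for transfers.

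**Working it through.** The plan gives no sample size, event count or overlap rate, so there is no stated figure to reproduce. Everything below except the number of Trusts and the dates is an assumption.

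**1. Effect on standard errors.** Let N be the number of people, p the share with two records, and r the within-pair correlation of contributions to the score.

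- Naive variance of the score: proportional to N(1 + p).
- True variance: N(1 − p) + Np(2 + 2r) = N(1 + p + 2pr).
- Ratio: 1 + 2pr/(1 + p). The SE ratio is its square root, and the understatement is 1 − 1/(SE ratio).

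For p = 5%, r = 0.5: 1 + 0.05/1.05 = 1.0476; square root 1.0235; understatement 2.3%.

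| p | r | SE ratio | SE too small by | Actual two-sided alpha at nominal 0.05 |
|---|---|---|---|---|
| 2% | 0.5 | 1.010 | 1.0% | 0.052 |
| 5% | 0.5 | 1.024 | 2.3% | 0.056 |
| 10% | 0.5 | 1.044 | 4.3% | 0.061 |
| 2% | 1 | 1.019 | 1.9% | 0.055 |
| 5% | 1 | 1.047 | 4.4% | 0.061 |
| 10% | 1 | 1.087 | 8.0% | 0.071 |

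The rows with r = 1 are the bound: both records contribute identically.

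**2. What this could overturn.** In the worst row, a test needs |z| of 1.96 × 1.087 = 2.13 instead of 1.96. Only reported p-values between about 0.033 and 0.05 could change side. At p = 5%, r = 0.5, the threshold is 1.96 × 1.0235 = 2.006, and the range shrinks to about 0.045 to 0.05.

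**3. Simulation.** Set-up: 12,000 runs of 4,000 people, five equal Trusts, entry uniform over 7.25 years, hazard 0.08 per year, 40% troponin positive, true hazard ratio 2.5, second test at another Trust after a mean gap of 0.5 years, 30% of second results redrawn. The empirical SD over the naive SE was 1.010, 1.030 and 1.061 at p = 2, 5 and 10%, so SEs were too small by 1.0, 2.9 and 5.7%. The proportion dead was 33.2–33.3% by row and 33.3% by person. With twice the hazard in people who overlap (p = 5%), it was 35.1% against 34.4%.

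**4. Hazard ratio.** The same simulation gave 2.49, 2.47 and 2.44 against 2.50 with one row per person, which looks like dilution from duplication. It is not. A rerun at p = 10% without redrawing second results gave 2.51 pooled and 2.51 with one row per person. With redrawing, but with the hazard following the newer result, it gave 2.44 and 2.43. The drop comes from redrawing results while leaving the hazard tied to the first one. Duplicate rows alone do not cause it.

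**5. Would a remedy gain much?**

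- *Separate fits by Trust.* With five equal Trusts, intervals are √5 = 2.24 times as wide. That is a large price for an SE error of a few per cent. Five Trusts by eight age groups also means 40 hazard ratios, and differences between Trusts mix with differences between assays.
- *Matching centrally on year of birth and date of death.* Chance pairs ≈ 0.8 × N²/2 ÷ (2,647 days × 35 to 53 effective birth years), where N is now the number of death rows; true pairs = N × p/(1 + p). With 20,000 death rows and p = 5%: 1,140 to 1,727 chance pairs against 952 true ones, so 1,140/2,092 = 54% to 1,727/2,679 = 64% of flags are false. Deaths bunch later in the period, which multiplies chance pairs by about 1.24 (roughly 1,410 to 2,140). With 5,000 death rows the picture is better: 71 to 108 chance pairs against 238 true. Only people who died can be matched. A cluster-robust variance on those pairs recovers 57–58% of the SE shortfall in the base case.
- *A shared key.* This needs approval at five Trusts and a fresh extract. The stated freeze is 1st April 2017, while the title block reads "Updated: 04/07/2024". It could serve only a new data cut, and the documents mention none.

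**The case for a change.** The best case for a change is that the gap is one of definition, whatever its effect on the SE. Date zero, age at first test, the peak within an episode and the revascularisation window all depend on whether the unit is the person or the patient within a Trust. For a transfer, the answer can alter all four. Without a stated overlap, a reader cannot confirm that the effect is negligible. Local algorithms, and keys kept at source, do suggest that IDs differ between Trusts.

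Much of this stands. The plan is silent on the unit across Trusts, and the promised central duplicate check does not fill that silence. But local operation does not exclude a method common to all Trusts under the shared SOP, so the documents cannot show that IDs differ. If the ID is common, the analyst merges on it in the study copy and takes the first troponin at any of the five Trusts as date zero. If it is not, the only workable unit is the patient within a Trust, and possible double entry is reported as a limitation. Either course follows from the data received, and neither alters the planned models.

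The point on revascularisation is weaker. Data are drawn from each Trust's own systems, so a procedure at any hospital outside the five is missed as well. A common ID would cure only part of this. Using date of death as a linkage field also goes beyond the purpose recorded in the De-identification section, which is to evaluate mortality.

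**Conclusion.** The reading of the plan is right: it names no cross-Trust key, and a person could be counted twice unless the SOP prevents it. This is a missing detail that analysts fill sensibly once they know what the subject ID is. It is not a fault in the analysis.

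On assumed overlaps of 2 to 10%, SEs are too small by about 1 to 4% by formula (r = 0.5), 1 to 6% by simulation, and 8% at the bound. In this simulation the crude proportion dead barely moves unless overlapping patients have a different mortality, and duplicate rows alone do not dilute the hazard ratio. No planned conclusion is shown to change. The stronger remedies either more than double interval width or rest on matches that can be mostly false and cover only people who died. Statisticians and governance teams could reasonably decline them.

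The conclusion rests on overlap staying within the assumed range, which the documents can neither confirm nor refute. Much heavier overlap combined with distinct IDs would make the limitation more serious, but it would still be one to report.

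### The study extract keeps no entry year, and the assay-specific hazard ratios have no common follow-up horizon; a 1-year cut would remove most of the resulting artefact without needing dates

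*Combined protocol and SAP*

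**What the plan says.** **Dates.** Under TROP-RISK STUDY dataset, the plan describes further de-identification: "This includes further de-identification to remove dates". The mechanism follows: "Dates will be converted to delta dates, with date zero being the date of the first troponin test". For other events, "All further dates are provided as number of days from date zero", and for the outcome, "Date of death will be converted to the number of days since date zero". No calendar year of entry is listed as retained.

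**Entry and follow-up.** Under Handling of troponin data, patients enter "between 2010 (2008 for University College Hospital) and 1st April 2017". All are followed "until death or censoring on 1st April 2017". Accrual is therefore long, with one fixed closing date.

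**Analysis.** Under Relationship between troponin positivity, age and mortality, the plan will "stratify the hazard ratios for troponin positive versus negative groups across these age groups by troponin assay", contrasting contemporary with high-sensitivity assays. It gives no common time horizon, no entry-period term and no Trust term.

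**What is kept at source.** Table 1 shows that the central database holds year of birth and the full date of death. A frozen copy is kept, and under Database management the Trusts can re-extract from their primary systems. The De-identification section makes the removal of dates deliberate: researchers are not to be able to work out a full date of death.

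**The concern.** With a fixed closing date, entry year determines how long a patient can be followed. It may also track background mortality and the assay in use. If high-sensitivity assays came later, that group has shorter follow-up. A Cox hazard ratio is then an average over a different stretch of time in each assay group. Where the excess risk of a positive troponin is concentrated early, the group with shorter follow-up shows the larger hazard ratio even if the assays perform identically. A reader of the assay-stratified results could take that for a difference between assays.

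The obvious adjustment, stratifying by entry year, is not available in the extract as described, because entry year is missing according to the primary outcome. It is known for survivors and only bounded for patients who died.

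**Working it through.** The plan states no sample size, event count or hazard ratio, so there is no figure to reproduce. The check has three parts.

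**1. What can be recovered from the extract.** Inputs from the plan: closing date 1 April 2017; entry from 2010, or 2008 at one centre (1 January assumed).

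- The entry window is 2,647 days (7.25 years), or 3,378 days (9.25 years) at the 2008 centre.
- Survivors: entry = 1 April 2017 minus follow-up days. For example, 1,000 days gives 6 July 2014, exactly.
- Patients who died on day *t*: entry lies between the window start and 1 April 2017 minus *t*.

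| Death on day | Possible entry years | At the 2008 centre |
|---|---|---|
| 30 | 8 | 10 |
| 365 | 7 | 9 |
| 1,825 | 3 | 5 |
| 2,500 | 1 | 3 |

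**2. Unequal follow-up by assay type.** Assumptions, none from the plan: uniform entry from 2010 to April 2017; contemporary assay until mid-2013 and high-sensitivity after; 30% positive; hazard in negatives 0.25 per year for 90 days, then 0.06; hazard ratio 3 for 90 days, then 1.4, the same for both assays.

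Potential follow-up is then uniform on 3.75 to 7.25 years (mean 5.50) for contemporary assays and on 0 to 3.75 years (mean 1.88) for high-sensitivity assays. Let *y*₀(*t*) and *y*₁(*t*) be the proportions negative and positive still at risk (share × survival × probability of being uncensored), and *d*₀, *d*₁ the matching death rates. The large-sample Cox estimate β solves

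∫ [ *d*₁ − (*d*₀ + *d*₁) · *y*₁e^β / (*y*₀ + *y*₁e^β) ] d*t* = 0.

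| Follow-up used | Contemporary | High-sensitivity | Gap |
|---|---|---|---|
| All | 1.725 | 2.062 | 0.337 |
| Truncated at 1 year, no dates used | 2.358 | 2.414 | 0.056 |
| Truncated at 1 year, only patients with at least 1 year of potential follow-up | 2.358 | 2.358 | 0 |

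The reason is the share of deaths in the first 90 days: 26% versus 49% over all follow-up, but 68% versus 71% within 1 year. Truncation alone removes 1 − 0.056/0.337 = 83% of the gap. Simulation of the same switch and hazard-ratio pattern gave 1.73 versus 2.07 untruncated and 2.38 versus 2.42 at 1 year.

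Varying the early hazard in negatives from 0.15 to 0.30 per year gives untruncated pairs from 1.61 versus 1.87 to 1.78 versus 2.14 (gaps 0.26 to 0.36). The 1-year gaps are 0.05 to 0.06. If the hazard ratio is constant over time, no gap arises.

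**3. Period confounding of the pooled hazard ratio.** This is the part that does need entry year. Assumptions: true hazard ratio 1.80; mortality falling 3% to 10% per entry year; positivity rising from 25% to 35–45%. The same equation, with baseline hazard 0.06 to 0.12 per year, gives an unstratified hazard ratio of 1.74 to 1.79; simulation gave 1.73 to 1.80. The largest shift is 1 − 1.73/1.80 = 3.9%.

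**The case against.** The strongest reply is that the larger number has little to do with the missing dates. It comes from a hazard ratio that changes over time, averaged over unequal follow-up. The remedy uses only observed time and status, and the extract has both. That stands. A reader might infer that the assay comparison cannot be checked or adjusted without entry year; part 2 shows otherwise. Only the last 0.056 of the gap needs potential follow-up. It cannot be removed by dropping recent survivors alone, because that would select on the outcome.

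A reader might also infer that period effects are inseparable from assay or Trust effects. The documents do not support this as a general statement:

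- They give no assay switch dates. The description of assays by Trust fits differences between Trusts as well as changes over time.
- The planned contrast is positive versus negative within assay type. No direct comparison of mortality between assay types is specified.
- Dates are removed from the extract, not from the source. If year of birth were released alongside age, entry year would be known to within about a year for patients who died too; the plan does not say whether it is.

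Finally, losing potential follow-up does not bias Kaplan-Meier, log-rank or Cox analyses, which do not use it.

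What remains is that no common horizon is stated, and that the extract as specified allows no period adjustment among patients who died.

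**Conclusion.** The point holds in a limited form, as something to consider. The extract lacks entry year for most patients who died, so entry period cannot be a covariate or stratum, and the plan sets no common horizon for hazard ratios that it will show side by side by assay type.

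If assay type tracks calendar time and the hazard ratio falls with time, identical biology could read about 1.7 versus 2.1. Both conditions are assumptions. The second is plausible, since the plan itself describes high short-term mortality in acute coronary syndromes. A 1-year horizon reduces the gap to about 0.04 to 0.06. The bias that only entry year can remove is at most about 4% of the pooled hazard ratio under the trends assumed.

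**What to change.** 1. **Common horizon.** State that the contemporary and high-sensitivity hazard ratios will also be reported with observed follow-up truncated at one common time, such as 1 year, next to the full-follow-up results. This needs no new data. Its cost is that later deaths do not contribute and that the 1-year hazard ratio is a different quantity from the full-follow-up one (about 2.4 against 1.7 to 2.1 in the example), so the two need separate labels.

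2. **Entry year.** State whether year of first troponin (YYYY, or a wider band) will be derived before dates are removed. If so, stratify the Cox models by it, at least as a sensitivity analysis. This would also allow restriction to patients with a given potential follow-up. It costs one field and one stratum term, for a small expected gain. The file becomes slightly more disclosive: entry year plus days to death places a death within a window of about a year, though not on a date. Year-level precision is already accepted for birth, and survivors' entry dates can already be derived. Because the handling of dates was agreed with each site's information governance office, the added field may need their agreement.
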